The objective of this study is to determine if participation in an FES-rowing exercise program can better preserve bone density in the lower limbs of individuals with spinal cord injury than have others types of activities or rehabilitation strategies. Previous literature studies using animals and computer models suggest that the repetitive mechanical stimulation derived from regular participation in a FES-rowing program may be sufficient to attenuate bone loss following SCI. No further animal studies or computer models can confirm the actual benefit in humans, therefore there is no other way to obtain this information without using human subjects.

2. Study Procedures

a) Please SUMMARIZE the research procedures, screening through closeout, which the human subject will undergo. Refer to sections in the protocol attached in section 16, BUT do not copy the clinical protocol. Be clear on what is to be done for research and what is part of standard of care.

In this study we expect to enroll a total of 10 participants with SCI. Five participants will be assigned to a Standard-of-Care (control) group and five participants will be assigned to an FES-rowing intervention group. Group assignment will be partly based on the preference of each potential participant and their willingness to make the necessary time commitment required for participation in a given group, with the added goal, to the extent possible, of matching the two groups for age, gender and time since injury. Only those individuals who have a strong desire to participate in a regular exercise program and who express a willingness to travel to VA Palo Alto the necessary number of times per week to perform FES-rowing will be potential candidates for inclusion in the rowing group.

Bone density measurements for both the Standard-of-Care group and the FES-rowing group will be performed using Dual energy X-ray Absorptiometry (DXA) and peripheral Quantitative Computed Tomography (pQCT). The Standard-of-Care group will undergo no other research procedures.

Title : Skeletal Health in the Lower Limbs Following Spinal Cord Injury
Approval Period: 01/13/2015 - 09/02/2015

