- g) **Study Endpoint. What are the guidelines or end points by which you can evaluate the different treatments (i.e. study drug, device, procedure) during the study? If one proves to be clearly more effective than another (or others) during the course of a study, will the study be terminated before the projected total participant population has been enrolled? When will the study end if no important differences are detected?**

The goal of this pilot study is to obtain preliminary data for five subjects participating in a 36-week FES-rowing group. Because of the small number of subjects, it is important to acquire data for all subjects and for all time points in order to determine the best estimates for key descriptive statistics including the mean, standard deviation and range of bone density changes. The study will not end until five subjects have completed the 36-week FES-rowing program.

3. Background

- a) **Describe past experimental and/or clinical findings leading to the formulation of the study.**

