The identification of potential participants from VA Palo Alto will be facilitated by [name], who is an Attending Physician in the Spinal Cord Injury Service at VA Palo Alto, and by [name], who is the Director of Clinical Research in the VA Palo Alto Spinal Cord Injury Center. In the course of performing their standard clinical responsibilities, both [name] and [name] are in regular contact with inpatients and outpatients in the VA SCI Center. Clinical colleagues of Drs. [name] and [name] whom we will tell about our planned study, will also assist in identifying potential subjects during the course of their standard clinical interactions with patients. A similar situation exists for [name] who is the Chief of Spinal Cord Injury at the Santa Clara Valley Medical Center in San Jose. Any patients who appear to be possible candidates for the study will be told briefly about the study by Drs. [name] and [name], or by their clinical colleagues, and if a patient expresses an interest in the study, they will be given contact information for [name]. Interested patients will be able to ask any additional questions by contacting [name].

- h) Inclusion and Exclusion Criteria.
Identify inclusion criteria.**

Subjects in the rowing groups:
· male and female SCI outpatients or inpatients
· have a T1 to T12, ASIA-A or ASIA-B, spinal cord injury
· be at least 18 year old

Title : Skeletal Health in the Lower Limbs Following Spinal Cord Injury
Approval Period: 01/13/2015 - 09/02/2015

- have their physician's clearance to exercise
- between 3 and 12 months post spinal cord injury
- minimum passive hip flexion range of motion (ROM) from 20 to 100 deg
- minimum passive knee flexion ROM from 20 to 100 deg
- minimum passive ankle ROM from +10 deg (dorsi-flexion) to -15 deg (plantar-flexion)
- currently use a manual wheelchair
- be able to perform independent and safe transfers to and from their wheelchair

Subjects in the control group:

- male and female SCI outpatients or inpatients
- have a C5 to T12, ASIA-A or ASIA-B, spinal cord injury
- be at least 18 year old
- between 3 and 12 months post spinal cord injury
- be able to perform safe transfers to and from their wheelchair, either independently or with assistance

Identify exclusion criteria.

Exclusion Criteria

- pregnant women
- women of childbearing potential not practicing a reliable method of contraception
- women who are post-menopausal
- have mechanical instability of the spine

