- a) For the following categories include a scientific estimate of the frequency, severity, and reversibility of potential risks. Wherever possible, include statistical incidence of complications and the mortality rate of proposed procedures. Where there has been insufficient time to accumulate significant data on risk, a statement to this effect should be included. (In describing these risks in the consent form to the participant it is helpful to use comparisons which are meaningful to persons unfamiliar with medical terminology.)

The risks of the Investigational devices.

This study will use an Odstock 4-channel muscle stimulator (model O4CHS) that has been used for many years in FES-rowing research studies in England, Canada and the United States. This device is powered by a standard, 9-volt battery identical to those used to power a transistor radio or smoke alarm. Our research consultants in England who are pioneers of FES-rowing programs, and who have helped establish FES-rowing programs in several other research laboratories around the world, have used this exact 4-channel stimulator with approximately 30 subjects with SCI and have never had an adverse event related

Title : Skeletal Health in the Lower Limbs Following Spinal Cord Injury
Approval Period: 01/13/2015 - 09/02/2015

to its use. Researchers at Spaulding Rehab in Boston also have never experienced an adverse event related to the use of the O4CHS device. Given the long history of safe use of the O4CHS device in other FES-rowing programs we believe this device qualifies as a non-significant risk.

The Odstock 4-channel muscle stimulator is used during FES muscle conditioning, FES muscle strength testing, and FES rowing.

The risks of the Investigational drugs. Information about risks can often be found in the Investigator's brochure.

None.

The risks of the Commercially available drugs, reagents or chemicals. Information about risks can often be found in the package insert.

None.

The risks of the Procedures to be performed. Include all investigational, non-investigational and non-invasive procedures (e.g., surgery, blood draws, treadmill tests).

Other than the bone density scans for which the risk is described later, there are no other procedures to be performed on the Standard-of-Care (control) group.

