5) Lower limb fracture during muscle conditioning, strength testing or FES-assisted rowing: The use of FES to stimulate paralyzed muscles in individuals with SCI has been studied for more than 50 years. Over that 50-year period there have been two reported cases of a fracture related to the use of functional electrical stimulation. One individual fractured their patella and a second individual fractured their lateral femoral condyle. Although the total number of individuals with SCI who have used functional electrical stimulation to exercise the lower limbs is not known, we believe the risk of a fracture is very low given that there have only been two reported fractures in 50 years of FES use. To further reduce the risk of fracture, only participants who have never experienced a low-energy or fragility fracture will be allowed to take part in this study. In addition, we will measure bone density for each participant at the beginning of the study and those measurements will provide us with an initial assessment of the health of each participant's femur and tibia. If we believe a participant's bones are too weak to safely undergo the muscle conditioning and rowing exercise, that participant will be withdrawn from the study.

6) Increase in neuropathic pain to an unacceptable level: Some spinal cord injured individuals suffer from neuropathic pain which can range from a mild tickling sensation to a severe burning sensation. It is not known what effect, if any, electrical stimulation has on this condition. In addition, some individuals with SCI who have some sensation in their thighs may find the electrical stimulation to be uncomfortable or even intolerable. Any participant who finds the electrical stimulation to produce neuropathic pain or sensation that is unacceptable to them will be withdrawn from the study.

7) Increase in spasticity to an unmanageable level: It is not known what effect FES has on the intensity and frequency of spasticity. In other FES-rowing programs, a few participants have had an increase in spasticity, while some participants have had a decrease. In general, spasticity levels should be reduced after a muscle conditioning or rowing session, since the muscles will be fatigued. If a subject experiences increased spasticity to a level that is unmanageable, they will be withdrawn from the study.

The risks of the Radioisotopes/radiation-producing machines (e.g., X-rays, CT scans, fluoroscopy) and associated risks.

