Confidentiality of the identifiable information will be carefully protected and data security measures will be strictly enforced. Any information or data on paper, including signed consents, will be stored in locked cabinets in locked offices in a secure VA building. All electronic data that contain identifiable subject information will be saved on a secure VA file server behind the VA firewall. No data will be maintained on portable electronic devices.

Protecting against and minimizing potential risks: To reiterate, the following are the potential risks to participants in the FES-rowing group.

- 1) Soft tissue reaction during FES training
- 2) Muscle strain during muscle conditioning, strength testing or FES-assisted rowing
- 3) Fall during transfer to or from rowing machine
- 4) Serious autonomic dysreflexia (AD) during FES training
- 5) Lower limb fracture during muscle conditioning, strength testing or FES-assisted rowing
- 6) Increase in neuropathic pain to an unacceptable level
- 7) Increase in spasticity to an unmanageable level

The following paragraphs describe how these risks will be mitigated to reduce them to the lowest possible levels.

1) Soft tissue reaction: Other than the typical reddening beneath the electrodes, which is to be expected, we will be vigilant to look for other types of soft tissue reactions and we will encourage all participants to be vigilant. To the best of our knowledge no prior FES-rowing participants have experienced a skin breakdown or pressure sore caused by their participation in an FES-rowing program. Nevertheless, before and after each session, we will look for any signs of bruising or swelling that might be suggestive of tissue breakdown, paying particular attention to the shoulders, back, buttocks, upper calves and knee areas.

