The risk of an AD response should also decrease as training progresses and a participant's muscles become conditioned from the electrical stimulation. Thus, the risk of AD will be highest during the initial muscle conditioning session. During the initial muscle conditioning session for each participant, we will pay particular attention to any signs of an AD response. At the first sign of an AD response, electrical stimulation will be stopped. Additional medical treatment (e.g., the application of Nitropaste) in the case of a severe AD response will be available in our research facilities. Given that no other FES-rowing group has ever reported a severe AD response we believe the likelihood of a participant having a severe AD response is very low, however, all of our research staff and each participant will be informed about the possibility of AD response and we will be vigilant in looking for an AD response.

5) Lower limb fracture during muscle conditioning, strength testing or FES-assisted rowing: To reduce the risk of fracture, only participants who have never experienced a low-energy or fragility fracture will be allowed to take part in this study. In addition, we will measure bone density for each participant at the beginning of the study and those measurements will provide us with an initial assessment of the health of each participant's femur and tibia. If we believe a participant's bones are too weak to safely undergo the muscle conditioning and rowing exercise, we will not allow that participant to continue in the study. In addition, participants will be educated on potential signs of a fracture for a person with SCI who is insensate in the area; these include localized redness and swelling, excess spasticity, possibly excess sweating and/or AD. We believe this is unlikely, but the added precaution of educating the participant will allow him/her to be extra vigilant for this occurrence.

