6) Increase in neuropathic pain to an unacceptable level: Some spinal cord injured individuals suffer from neuropathic pain which can range from a mild tickling sensation to a severe burning sensation. It is not known what effect, if any, electrical stimulation has on this condition. In addition, some individuals with SCI who have some sensation in their thighs may find the electrical stimulation to be uncomfortable or even intolerable. Any participant who finds the electrical stimulation to produce neuropathic pain or sensation that is unacceptable to them will be withdrawn from the study.

7) Increase in spasticity to an unmanageable level: It is not known what effect FES has on the intensity and frequency of spasticity. In other FES-rowing programs, a few participants have had an increase in spasticity, while some participants have had a decrease. In general, spasticity levels should be reduced after a muscle conditioning or rowing session, since the muscles will be fatigued. If a subject experiences increased spasticity that is unmanageable, they will be withdrawn from the study.

- d) **Explain the point at which the experiment will terminate. If appropriate, include the standards for the termination of the participation of the individual participant Also discuss plans for ensuring necessary medical or professional intervention in the event of adverse effects to the participants.**

Given the low risk level and given the success of other FES-rowing research studies, we do not anticipate

Title : Skeletal Health in the Lower Limbs Following Spinal Cord Injury
Approval Period: 01/13/2015 - 09/02/2015

terminating the study before the two-year funding period ends.

However, individual participants may be withdrawn from the study for several reasons, including, but not limited to:

- Inadequate muscle response to electrical stimulation
- Severe AD reaction in response to exercise or electrical stimulation
- Markedly low bone density compared to other individuals with acute and sub-acute SCI
- An increase in neuropathic pain or pain sensation from electrical stimulation to an unacceptable level
- An increase in spasticity to an unmanageable level

e) **Data Safety and Monitoring Plan (DSMP).** See guidance on **Data Safety and Monitoring.**

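### As most naturally read, the baseline-scan withdrawal rule selects rowers but not controls on bone density, and sections 9(a), 9(c) and 9(d) do not settle which group it covers

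*Combined protocol and SAP*

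**What the plan says.** Both groups have DXA and pQCT at baseline and at the end of weeks 8, 22 and 36 (section 4(c)). The baseline scan has two uses.

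- **Outcome.** It is time 0 for the quantities that section 2(g) sets out to estimate: "the mean, standard deviation and range of bone density changes".
- **Safety.** Under 9(a), item 5, if the investigators believe a person's "bones are too weak to safely undergo the muscle conditioning and rowing exercise, that participant will be withdrawn from the study". Section 9(c), item 5, repeats this: "we will not allow that participant to continue in the study". No threshold, skeletal site or scanner is named.

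Item 5 belongs to a list that 9(a) opens with the rowing group's programme and that 9(c) introduces with "the following are the potential risks to participants in the FES-rowing group". For controls, 2(a) states "The Standard-of-Care group will undergo no other research procedures", and 9(a) says that apart from the scans "there are no other procedures to be performed on the Standard-of-Care (control) group".

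Section 9(d) lists reasons for which individual participants may be withdrawn, among them "Markedly low bone density compared to other individuals with acute and sub-acute SCI". It does not say which group this concerns.

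Assignment depends partly on preference, with matching where possible on age, gender and time since injury (2(a)). Neither group's inclusion list in 8(h) mentions bone density.

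**The concern.** The wording of 9(a) and 9(c) is a test of fitness to train and row, which has no obvious application to a control. If it is applied as worded, a would-be rower with weak bones leaves before training, while a control with the same scan stays. Section 2(g) keeps the study open until five rowers complete, so a rower removed in this way would in effect be replaced by one who passes. No equivalent rule is stated for controls.

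The two groups could then differ in baseline bone density because of the rule itself, even if matching on age, gender and time since injury succeeds. If later change is related to starting level, part of any rowing-control difference in change would be selection. The documents describe no adjustment for baseline bone density and no listing of withdrawn participants. With five per group, one person is 20% of a group, so a single retained low-density control can visibly move the mean, SD and range.

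**Working it through.** **Which group does the rule reach?**

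| Place | Standard | Group |
|---|---|---|
| 9(a), item 5 | too weak for conditioning and rowing | not named in the sentence; list introduced for the rowing group |
| 9(c), item 5 | same | list headed as rowing-group risks |
| 9(d) | low relative to peers with recent injury | not named; withdrawal is optional |
| 8(h) inclusion lists | no bone-density condition | both |
| 8(h) exclusion list | low-trauma lower-limb fracture since injury | both |

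The first two rows point to rowers. The third uses a different standard and could reach a control. Its four companion reasons concern muscle response, autonomic dysreflexia, pain and spasticity under stimulation or exercise, which again suggests rowers but does not settle it.

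**How large could one-sided selection be?** The plan gives no threshold, SD, correlation or power calculation, so there is no figure of its own to reproduce. What follows is illustration on assumptions: baseline bone density is normal, and the lowest fraction q of would-be rowers is removed while controls are untouched.

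- Shift in the rowers' mean baseline = φ(z_q)/(1 − q), in SD of baseline.
- Chance that at least one of five controls lies in the range removed from the rowers = 1 − (1 − q)^5.
- Induced difference in mean change = r × baseline shift, in SD of change, where r is the baseline-change correlation. Positive r means that a higher baseline goes with less later loss.

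| q | Baseline shift (SD) | At least one of 5 controls | Change shift, r = ±0.3 | Change shift, r = ±0.5 |
|---|---|---|---|---|
| 5% | 0.109 | 23% | ±0.033 | ±0.054 |
| 10% | 0.195 | 41% | ±0.058 | ±0.097 |
| 20% | 0.350 | 67% | ±0.105 | ±0.175 |
| 30% | 0.497 | 83% | ±0.149 | ±0.248 |

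Worked line, q = 20%: z = −0.842, φ(z) = 0.280, and 0.280/0.80 = 0.350. With r = 0.5 the change shift is 0.175. With r = 0 it is zero at every q.

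A simulation for q = 10%, 20% and 30% with r = ±0.5 agreed with these values to within 0.01 SD. When the same cut was applied to both groups, the differences in baseline and in change fell to within 0.01 SD of zero.

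**Scale.** With unit SD, the standard error of a 5 v 5 difference is √(1/5 + 1/5) = 0.63 SD. At an assumed two-sided 5% level and 80% power, five per group detect about 2.02 SD by the t distribution (1.77 SD by the normal formula).

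**The case against.** Five points can fairly be made against this.

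- **One-sidedness is inferred.** A reader might conclude that controls are exempt. The documents never say so, and 9(d) read literally could cover them. This stands: the firm textual finding is that the sections leave the rule's reach open, with rowers-only as the natural reading.
- **Part of the fragility screen is shared.** The fracture exclusion applies to both groups. This also stands, but that exclusion concerns fracture history, not the density seen on the scan.
- **The rule acts on level, and the outcome is change.** A reader might infer a bias in favour of rowing. The documents do not support that. People with low density may continue to lose quickly (positive r, flattering rowing) or may have less left to lose (negative r, hiding a benefit), and no correlation is given.
- **The effect may be small or absent.** At q = 5%, the chance that none of the first five would-be rowers is removed is 0.95^5 = 77%. Even the largest illustrated shift, 0.25 SD, is well below the 0.63 SD standard error. Preference-based assignment and the different injury levels admitted (C5-T12 for controls, T1-T12 for rowers) are differences that need no trigger. This limits the importance of the point, but those differences are built into the design, whereas this one can be made visible on paper.
- **This is a descriptive pilot.** No between-group test is stated. Yet there is a control group, and 1(b) says that better preservation than previously reported would be clinically important, so readers will make the comparison.

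A further tempting step is to say that screened rowers would be set against unscreened patients in earlier reports. The documents do not say whether those studies screened on bone density, so that claim is not made here.

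**Conclusion.** The concern holds in limited form. As most naturally read, 9(a) and 9(c) select rowers on baseline bone density and leave controls unselected, and nothing described in the plan corrects or displays this. Section 9(d) leaves the rule's reach uncertain, so the three places must be reconciled.

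The rowing-control difference in bone change may partly reflect this selection. It cannot be said that it will, or in which direction. If the lowest 5-30% were removed, the rowers' mean baseline would rise by 0.11-0.50 SD, and the difference in change would move by 0.03-0.25 SD either way for correlations of 0.3-0.5 in absolute value. The normal distribution, the removal rates and the correlations are all assumptions. This is a modest reporting and clarity problem that is cheap to fix; it does not invalidate the pilot.

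**What to change.** 1. Reconcile 9(a), 9(c) and 9(d) on which group the bone-density rule covers and by which of the two standards. The clinical rule itself is for the investigators to decide.
2. Record the same bone-density judgement from the existing baseline scan for every participant in both groups, before training starts and before any later scan is seen. Participants sign group-specific consents (13.2, 13.3), so group will usually be known by then; fixing the time of the record is what protects it.
3. Report the rowing-control comparison with all controls, and again with only the controls who pass that judgement. Show individual baseline values, and list any withdrawn rower with the baseline value.
4. State in 1(b) and 1(c) that conclusions apply to people whose bone density allowed them to start rowing.

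The cost is protocol wording and slightly more reporting, with no added visit, scan or radiation. There are two drawbacks. A subjective judgement is recorded for controls, and the restricted comparison will be very small. For that reason it should stand beside the all-controls comparison and not replace it.
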